- 2. Standard of Care (SOC) with Dehydrated Human Amnion/Chorion Membrane (dHACM).

Neither the patients nor the clinicians will be blinded to group assignments. The randomization will follow a balanced schedule, using permuted blocks of 12. When a patient will be ready for randomization, the study site will contact a representative from the sponsor, who will open a sequentially numbered opaque envelope to disclose the group assignment, maintaining allocation concealment.

Throughout the 4-week treatment phase, patients will be reassessed on days 7, 10, 14, 17, 21, and 28. The SOC dressing applied in both groups consisted of a three-layer system:

- First layer: Non-adherent, porous paraffin gauze.
- Second layer: Absorbent gauze pads.
- Third layer: Soft roll and Crepe bandage.

Note:

- a. 2 sizes of HPTC used:
- i. 0.8 in x 1.6 in or 2 cm x 4 cm (8 sq cm)
- ii. 1.6 in x 1.6 in or 4 cm x 4 cm (16 sq cm)
 - b. 2 sizes of dHACM used:
- i. 5 cm x 5 cm (25 sq cm)
- ii. 8 cm x 6 cm (48 sq cm)

If the study ulcer was found to be 100% re-epithelialized during the visit, no further study procedures will be conducted at that time. The patient will then be scheduled for a follow-up visit after one week to confirm the healing.

If full healing was not achieved, an evaluation will be carried out to check for any signs of clinical infection. If an infection is confirmed, treatment with topical antimicrobials or oral antibiotics will be permitted, though the use of topical antibiotics will be prohibited. After this infection assessment, the ulcer would be cleaned, photographed, and debrided at the investigator's discretion to ensure a clean and granulating wound base with minimal adherent slough. The Standard of Care (SOC) will be then re-applied, and patients will be instructed to keep the bandage dry. Additionally, they will be advised to contact or return to the study site if the bandage became soiled or removed.

Study Completion:

Patients will complete the study 4 weeks after their initial treatment visit. However, if a patient's study ulcer healed before the 4-week period, they will be considered to have completed the study at the time of full healing.

Complete healing will be defined as 100% re-epithelialization of the ulcer with no drainage. Throughout the study, patients will retain the right to decline participation or withdraw at any time without prejudice.

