In the event of a patient's withdrawal, their last recorded wound measurement will be carried forward to determine the change in wound size and calculate their final outcome.

Study Outcomes:

Primary Endpoint:

• The primary outcome of the study will be the proportion of subjects who achieved improvement in wound healing, as observed on days 7, 10, 14, 17, 21, and 28. The wound closure of the target ulcer will be continuously monitored until the end of the 4-week period.

Secondary Endpoints:

- **Time to Achieve Complete Wound Closure:** Time taken for the target ulcer to achieve complete wound closure will be assessed on days 7, 10, 14, 17, 21, and 28.
- **Percentage Wound Area Reduction:** This will be measured weekly on days 7, 10, 14, 17, 21, and 28 using digital photography.
- **Mean Number of Repeated Applications of HPTC:** The average number of times the reapplication of High Purity Type-I Collagen-based Skin Substitute (HPTC) to achieve wound closure will be documented as part of the study process.

Exploratory Endpoint:

• The appearance, structural stability, and fragility of the newly formed skin will be documented at each visit. Any recurrence of the wound will also be monitored.

Subjects must be at least 18 years of age or older.	A subject known to have a life expectancy of less than 6 months.
Subjects must have a diagnosis of type 1 or 2 diabetes mellitus.	If the target ulcer is infected or if there is cellulitis in the surrounding skin.
At enrolment, subjects must have a target diabetic foot ulcer with a minimum surface area of 5.0 cm ² and a maximum surface area of 10.0 cm ² , measured post-debridement using a ruler.	Presence of osteomyelitis or exposed bone, probes to bone or joint capsule on investigator's exam, or radiographic evidence.
The target ulcer must have been present for a minimum of 4 weeks and a maximum of 52 weeks of standard care prior to the initial screening visit.	A subject that has an infection in the target ulcer that requires systemic antibiotic therapy.
The target ulcer must be located on the foot, with at least 50% of the ulcer below the malleolus.	A subject receiving immunosuppressants (including systemic corticosteroids at doses greater than 10 mg of prednisone per day or equivalent) or cytotoxic chemotherapy.
The target ulcer must be full thickness on the foot or ankle and must not probe to bone.	Topical application of steroids to the ulcer surface within one month of initial screening.

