Descriptive statistics will be used to summarize the data. Quantitative data will be presented as means or medians, while qualitative data will be expressed as frequencies and percentages. The study aims to assess the proportion of study participants achieving wound healing by the end of the fourth week. To measure the proportion of participants showing improvement in wound healing, observations will be conducted on days 7, 10, 14, 17, 21, and 28. The proportion of participants achieving wound healing would be compared between both the groups using Chisquare/ Fisher's exact test. Additionally, the average reduction in ulcer size from baseline to the end of the fourth week will be compared between groups, and the significance of the reduction will be analysed using the independent t test/Mann-Whitney U test.

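### Time to complete closure is a secondary endpoint, but the analysis section gives it no between-arm test and no rule for ulcers that never close

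*Combined protocol and SAP*

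**What the plan says.** The Secondary Endpoints section of the combined protocol and SAP says: "Time taken for the target ulcer to achieve complete wound closure will be assessed on days 7, 10, 14, 17, 21, and 28". Study Completion defines complete healing as full re-epithelialization without drainage.

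The Statistical analysis section makes two between-arm comparisons. One is for healing status: "The proportion of participants achieving wound healing would be compared between both the groups", by chi-square or Fisher's exact test. The other is for ulcer size: "the significance of the reduction will be analysed using the independent t test/Mann-Whitney U test". Closure time appears in neither. The only sentence that could cover it is generic: "Quantitative data will be presented as means or medians".

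Three other statements bear on it:

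- **End of follow-up.** "Patients will complete the study 4 weeks after their initial treatment visit"; for an ulcer that heals sooner, "they will be considered to have completed the study at the time of full healing".
- **Withdrawal.** The last wound measurement is "carried forward to determine the change in wound size and calculate their final outcome".
- **Confirmation.** After full re-epithelialization is seen: "The patient will then be scheduled for a follow-up visit after one week to confirm the healing".

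**The concern.** Follow-up stops at four weeks, so some ulcers may never have a closure time. A mean then needs either an imputed value for those patients or their exclusion. An all-patient median needs open ulcers ranked after every healer, and it is not reached if fewer than half close by day 28. The plan states none of these choices.

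The easiest default is to average the recorded closure times, which exist only for healers. Being a healer is itself an outcome of treatment, so the two groups averaged are no longer the randomised groups. An arm that heals more patients, including slower ulcers that would otherwise have stayed open, can show a similar or longer mean. The trial is open label, so a rule chosen after the data are seen is also hard to defend.

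**Working it through.** The plan has no figure to reproduce: it states no closure rates, sample size, alpha or power. What follows is an illustration.

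**Inputs.** From the plan: visits v = 7, 10, 14, 17, 21, 28 and balanced allocation. Assumed: closure by day 28 (p), a constant closure rate, closure dated to the next visit, 60 patients per arm, no withdrawals.

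**Formulas.** Daily rate h = −ln(1 − p)/28. Probability of closure at visit k: exp(−h·v(k−1)) − exp(−h·v(k)), with v(0) = 0. Let S be the sum of probability × visit day. Healer mean = S/p. All-patient mean, with open ulcers counted to day 28, = S + 28(1 − p).

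**50% vs 25% closed.**

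- p = 0.50: h = 0.0248, S = 7.56. Healer mean 7.555/0.50 = 15.11. All-patient mean 7.555 + 14 = 21.56.
- p = 0.25: h = 0.0103, S = 4.00. Healer mean 4.00/0.25 = 16.00. All-patient mean 4.00 + 21 = 25.00.

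The gap is 0.89 days among healers and 3.44 days in all patients.

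**Other assumed rates.** The last column is the share of simulated trials in which the better arm's healer mean is the longer one.

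| Closed by day 28 | Healer means (gap), days | All-patient means (gap), days | Wrong sign, healers |
|---|---|---|---|
| 40% vs 20% | 15.51 vs 16.14 (0.63) | 23.00 vs 25.63 (2.63) | 41% |
| 50% vs 25% | 15.11 vs 16.00 (0.89) | 21.56 vs 25.00 (3.44) | 37% |
| 60% vs 40% | 14.63 vs 15.51 (0.88) | 19.98 vs 23.00 (3.02) | 34% |
| 70% vs 50% | 14.04 vs 15.11 (1.07) | 18.23 vs 21.56 (3.33) | 28% |
| 90% vs 60% | 12.03 vs 14.63 (2.60) | 13.63 vs 19.98 (6.35) | about 5% |
| 95% vs 80% | 11.00 vs 13.25 (2.25) | 11.85 vs 16.20 (4.35) | about 4% |

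In the first four rows the all-patient mean has the wrong sign in 0.7% to 2.5% of trials.

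**Late separation.** Take the 25% arm and add 0.125 to the closure probability at each of days 21 and 28. Then S = 4.00 + 0.125 × 21 + 0.125 × 28 = 10.125. The healer mean is 10.125/0.50 = 20.25 days, against 16.00 in the worse arm. The better arm looks slower in about 95% of trials.

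**Power at 50% vs 25%, two-sided 0.05.** With constant rates: chi-square 82%, log-rank 82%, 28-day restricted mean 70%. With late separation: 82%, 73% and 12%.

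**Withdrawals at 50% vs 25%.** Suppose 20% withdraw, all from ulcers that would have stayed open. Censoring them at the last visit estimates 58% vs 28% closed. Counting them as unhealed to day 28 gives 50% vs 25%.

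**Confirmation dates.** Closure day + 7: 7→14, 10→17, 14→21 and 21→28 coincide with scheduled visits. 17→24 and 28→35 do not, and day 35 lies beyond the four-week end of study.

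**The case against.** - **No healers-only analysis is stated.** A reader might infer that the plan prescribes one. It does not; the plan leaves the choice open, and the harm above arises only if that choice is made.
- **The data would support a valid analysis.** A reader might infer that the trial cannot report a valid comparison of healing speed. That is too strong, because closure status at six visits is enough for a time-to-event analysis. The defect is that none is prespecified.
- **The event date is largely implied.** A reader might infer that it is undefined. The healing definition contains no confirmation step, closure time is assessed only at the listed visits, and a healed patient completes at healing. Together these point to the visit at which closure is first seen. What stays open is the effect of a failed or missed confirmation. The confirmation visit is scheduled individually, so an off-schedule day is not in itself a contradiction.
- **There is a withdrawal rule.** Carrying the last measurement forward appears to make an open withdrawal unhealed. It gives a size or status, however, and no closure or censoring time.
- **The size is assumed.** At high closure rates the reversal is uncommon. With a steeply rising closure rate (Weibull shape 3) at 50% vs 25%, the gaps are 0.6 days among healers and 1.5 days in all patients, so the contrast is smaller. No single size is supported.

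These points narrow the concern. None of them supplies an analysis for the endpoint.

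**Conclusion.** The concern holds as a prespecification gap in one secondary endpoint. Closure time has no named test, no rule for open ulcers, and no estimator beyond a generic mean or median that cannot be computed for all patients without a further, unstated rule. If the gap is filled by averaging healers, a real difference can be understated about three- to four-fold at moderate closure rates. Its direction can then be wrong in roughly 28% to 41% of trials, in 4–5% at high closure rates, and in about 95% when the arms separate only late. All these figures rest on assumed rates and 60 patients per arm; the existence of the gap does not.

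The primary comparison of proportions is untouched. A reader might also infer that a time-to-event test would gain power over the planned chi-square. The calculations do not show that: the two are about equal under constant rates, and log-rank is weaker under late separation. The gain is an interpretable secondary endpoint. This should be changed before analysis.

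**What to change.** Add to the Statistical analysis section:

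*Time to complete closure will be analysed in all randomised patients by Kaplan-Meier estimates and a log-rank test, with a Cox hazard ratio and 95% CI, as a secondary analysis beside the comparison of proportions healed. The event date is the scheduled visit at which complete re-epithelialization without drainage is first seen. Ulcers still open are censored at day 28. Patients who withdraw with an open ulcer are counted as unhealed to day 28; a sensitivity analysis censors them at their last visit.*

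The withdrawal rule follows the carry-forward rule already in Study Completion.

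Use one closure definition for this analysis and for the proportion healed, and state how a failed or missed one-week confirmation affects both. Otherwise the same reopened ulcer could count as healed in one analysis and open in the other. Reconcile the confirmation visit with study completion at healing or at four weeks, and with the exploratory endpoint that monitors recurrence.

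**Cost.** SAP wording, modest extra analysis, and an edit to align the visit and completion text. Because log-rank can lose power to chi-square when the arms separate late (73% vs 82% in the illustration), it should not replace the planned test.

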Title:

A Randomized, Controlled Clinical Trial Comparing the Use of High Purity Type-I Collagen-based Skin Substitute vs. Dehydrated Human Amnion/Chorion Membranein the Treatment of Diabetic Foot Ulcers

NCT Number:

NCT06470087

Date of the document:

31/10/2024

Title: A Randomized, Controlled Clinical Trial Comparing the Use of High Purity Type-I Collagen-based Skin Substitute vs. Dehydrated Human Amnion/Chorion Membrane in the Treatment of Diabetic Foot Ulcers

Introduction

Chronic wounds, especially diabetic foot ulcers (DFUs), place a significant financial strain on healthcare systems. In the United States, the estimated annual cost for treating these wounds is about \$30 billion. DFUs are the most prevalent form of lower extremity wounds, making up roughly 80% to 85% of such cases. Annually, between 6.5 and 7 million individuals in the U.S. are affected by chronic DFUs. With an aging population and increasing incidence of risk factors such as obesity and congestive heart failure, the prevalence of DFUs is expected to rise.

Chronic diabetic foot ulcers (DFUs) are linked to considerable suffering and a decline in quality of life, as the healing process is typically slow and painful. Even in optimal conditions, these ulcers can take weeks or months to recover, often experiencing a frustrating pattern of slow healing and repeated breakdown. Wound care specialists frequently encounter patients who have suffered from these ulcers for years, with some needing amputation as the only solution for pain relief.

Type-I collagen, when full, purified, and uncross-linked, offers 3,000 receptor sites per molecule for growth factors like fibroblasts to adhere to, making it an ideal matrix for wound healing. Type-I collagen shows 97% similarity across species, while Type-II and Type-III collagen only have 80% similarity within the same species. For instance, Type-I collagen in humans is quite similar to that in cows or birds. Furthermore, Type-I collagen is the least likely to provoke an immune response due to its lack of the sulfur-containing amino acid cysteine. In contrast, Type-II and Type-III collagen contain more cysteine, making them more immunogenic.

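### Recurrence and new-skin quality are exploratory endpoints, but the healing and completion rules allow only 0 to 7 days of observation after closure, where up to 21 days remain to day 28

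*Combined protocol and SAP*

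**What the plan says.** The Exploratory Endpoint paragraph (Study Outcomes) sets two tasks: "The appearance, structural stability, and fragility of the newly formed skin will be documented at each visit" and "Any recurrence of the wound will also be monitored". It gives no definition of recurrence and no window over which to count it. The Statistical analysis section names no analysis for either item.

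Four other places govern what happens once an ulcer closes:

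- **Study Treatment.** When the ulcer is found fully re-epithelialized, "no further study procedures will be conducted at that time". The text continues: "The patient will then be scheduled for a follow-up visit after one week to confirm the healing".
- **Study Completion.** The general rule is "Patients will complete the study 4 weeks after their initial treatment visit", but for patients who heal sooner, "they will be considered to have completed the study at the time of full healing". The same section states: "Complete healing will be defined as 100% re-epithelialization of the ulcer with no drainage". The one-week confirmation is not part of that definition.
- **Primary Endpoint.** Closure of the target ulcer is to be followed through to the end of week four.
- **Patient Screening and Eligibility.** There are only two phases, screening and treatment. No follow-up phase after healing is described.

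**The concern.** Recurrence can happen only after closure, and the stability and fragility of new skin matter most in ulcers that have closed. The completion rule takes patients out of the study at that point, so a stated rule defeats a stated endpoint. A site cannot both treat a patient as finished at healing and follow closure to week four. The confirmation visit also falls after the patient has, by the completion rule, already left the study.

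Two things are at stake. First, any statement about recurrence would rest on a week or less per closed ulcer, in a disease that the Introduction describes as "often experiencing a frustrating pattern of slow healing and repeated breakdown". Second, the Statistical analysis section compares healing by the end of the fourth week. An ulcer that closed on day 7, was confirmed on day 14 and reopened on day 18 would count as healed, and no planned visit would reveal the reopening.

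**Working it through.** The plan states no recurrence rate, healing rate or sample size, so it has no figure to reproduce. The check is arithmetic on visit days.

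**Inputs.** Visits are on days 7, 10, 14, 17, 21 and 28 (Patient Screening and Eligibility; Study Treatment). The confirmation visit is one week after closure is found (Study Treatment). Completion is at full healing, or otherwise at four weeks (Study Completion).

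**Assumption.** Closure is dated to the visit at which it is found, and visits occur on their nominal days.

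**Formulas**, for closure found on day *c*:

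- Completion rule read literally: days observed = 0.
- With the confirmation visit: days observed = 7, on day *c* + 7.
- Days remaining to day 28 = 28 − *c*.
- Days unused despite the confirmation visit = (28 − *c*) − 7, with a floor of 0.

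| Closure found (day) | Literal completion | Confirmation visit on day | Days remaining to day 28 | Days unused after confirmation | Share unused |
|---|---|---|---|---|---|
| 7 | 0 | 14 | 21 | 14 | 14/21 = 67% |
| 10 | 0 | 17 | 18 | 11 | 11/18 = 61% |
| 14 | 0 | 21 | 14 | 7 | 7/14 = 50% |
| 17 | 0 | 24 | 11 | 4 | 4/11 = 36% |
| 21 | 0 | 28 | 7 | 0 | 0 |
| 28 | 0 | 35 | 0 | 0 | – |

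If completion is taken literally, all of the remaining days are unused for any ulcer closing before day 28.

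The one-week visit lands on a scheduled day for closures on days 7, 10, 14 and 21. For closure on day 17 it lands on day 24, which is not a scheduled visit. For closure on day 28 it lands on day 35, after the four-week end.

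The text therefore supports three incompatible periods after closure: none, 7 days with one visit, or up to day 28. It does not say which applies. It also does not say whether skin quality or recurrence is recorded at the confirmation visit.

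**The case against.** The strongest reply is that the healed site is seen again. The one-week visit is explicit, early breakdown could be detected there, and if it counts as a visit for the exploratory endpoint, the new skin would be documented too. This stands. A reader might infer that both endpoints go wholly unobserved in closed ulcers, and the documents do not support that.

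The halt to procedures at the closure visit can also be read narrowly. The next paragraph lists the infection check, cleaning, photography, debridement and re-dressing for ulcers that have not healed, and the halt may refer only to these. Judging full re-epithelialization already means inspecting the new skin. This reading is reasonable, but the text does not settle it, so it should be written down. Likewise, every ulcer closing after day 7 has at least one earlier scheduled visit at which new epithelium could be described. It would be wrong to say that skin quality is captured only in slow healers.

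Two further inferences are tempting and fail:

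- *Recurrence will be near zero in both arms.* This needs an early recurrence rate, and the documents give none.
- *The plan flatters the faster-healing arm.* If each closed ulcer gets the same 7 days (or the same 0), the window per closed ulcer is equal between arms. A faster arm forgoes more potential days to day 28, but its recurrence is not measured over a shorter window.

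Finally, these are exploratory endpoints with no planned test, and the documents announce no durability claim. That limits the weight of the point but does not reconcile the conflicting sections.

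**Conclusion.** The point holds as a conflict between sections that cuts short the observation of a stated endpoint. Observation after closure is 0 days on the literal rule, or one visit about 7 days later. For closures found on days 7 to 17, between 4 and 14 of the remaining 11 to 21 days go unused even when the confirmation visit takes place. A reopening in that gap would not be seen. Closures on day 21 lose nothing if the confirmation visit is kept.

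How many patients this affects is unknown, because the plan gives no expected healing rate by day 17. The result rests on nominal visit days and on closure being dated to the visit that finds it. The change should be made, but it is not critical: the endpoints are exploratory. The reach into the week-four healing comparison is limited to ulcers that reopen before day 28. For the same reason, the plan leaves unclear whether an ulcer that fails its confirmation visit still counts as healed.

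**What to change.** Reconcile Study Treatment, Study Completion, and the Primary and Exploratory Endpoint paragraphs as follows. These changes concern assessment only.

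1. In Study Completion, replace completion at healing with continued attendance at the scheduled visits to day 28.
2. Keep the one-week confirmation visit for every closed ulcer and state that it is a study visit. This includes closures on day 17 (visit on day 24), day 21 (day 28) and day 28 (day 35).
3. State that the new-skin assessment is recorded at the closure visit and at each later visit, whatever other procedures stop.
4. Report recurrence per closed ulcer, by arm, over the common 7-day window. Also report it with days observed after closure, because under this change the windows are 21, 18, 14, 11, 7 and 7 days for closure on days 7, 10, 14, 17, 21 and 28. Listing the days discloses that imbalance but does not remove it, which is why the common window is needed.
5. Make no statement about durability beyond the observed window.

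The cost is protocol wording and a few short visits for early healers. The maximum is five, for closure on day 7 (days 10, 14, 17, 21 and 28), and one of these, day 14, is already the planned confirmation visit. Apart from day 24 and day 35, which the existing one-week rule already implies, all are days that patients agree at entry to attend. No new type of assessment, staff or patients are needed.

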The objective of this study is to evaluate and compare the safety and effectiveness of High Purity Type-I Collagen-based Skin Substitute (HPTC) with Dehydrated Human Amnion/Chorion Membrane (dHACM) for treating diabetic foot ulcers (DFUs). This randomized, controlled clinical trial seeks to provide valuable insights into the best treatment strategy for enhancing healing outcomes and reducing the challenges posed by chronic DFUs.

Materials and Methods

Study will be carried out as a randomized, controlled open-label study to evaluate the safety and effectiveness of High Purity Type-I Collagen-based Skin Substitute (HPTC) compared to Dehydrated Human Amnion/Chorion Membrane (dHACM) for treating diabetic foot ulcers (DFUs). The trial will include patients with DFUs treated by wound care specialists at Adichunchanagiri Institute of Medical Sciences, B. G. Nagara, under the supervision of primary investigator [name] consent will be obtained from all participants prior to any study-related procedures, and each patient will sign an Institutional Ethics Committee/Investigational Review Board (IEC/IRB)-approved consent form. The investigator will comply with regulatory guidelines and Good Clinical Practice (GCP) in

obtaining and documenting informed consent. All study products will be produced, handled,

and stored in accordance with Good Manufacturing Practices (GMP). Strict patient confidentiality protocols will be maintained throughout the study.

Patient Screening and Eligibility

The study population will consist of patients seeking treatment for DFUs. Eligible patients will be those willing to participate and comply with scheduled visits on days 7, 10, 14, 17, 21, and 28. The study will include two phases: screening and treatment. The screening phase aimed to determine patient eligibility for the treatment phase. The inclusion and exclusion criteria are detailed in Table 1. During screening, a series of assessments will be conducted, including demographics, medical history, concomitant medications, vital signs, physical examination, leg ulcer history, clinical infection signs at the ulcer site.

Study Treatment:

The treatment phase of the study will commence with a series of evaluations to ensure patients remained eligible. Participants who will continue to meet the inclusion criteria after the screening phase will be randomly assigned to one of two groups:

- 1. Standard of Care (SOC) with High Purity Type-I Collagen-based Skin Substitute (HPTC).

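### The primary healing comparison is unadjusted although ulcer duration and area are known before randomisation; the test stays valid overall, but precision and protection against chance imbalance are lost

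*Combined protocol and SAP*

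**What the plan says.** The Statistical analysis section gives one between-arm test for the primary proportion: "The proportion of participants achieving wound healing would be compared between both the groups using Chisquare" or Fisher's exact test. It names no covariate, stratified test or sensitivity analysis, and no rule for choosing between the two tests.

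Under Study Treatment, "The randomization will follow a balanced schedule, using permuted blocks of 12". No stratification factor is named.

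Table 1 sets the eligible range of the target ulcer. For duration: "The target ulcer must have been present for a minimum of 4 weeks and a maximum of 52 weeks of standard care". For area, measured after debridement: "minimum surface area of 5.0 cm ² and a maximum surface area of 10.0 cm ²". Assignment follows confirmation of eligibility: "Participants who will continue to meet the inclusion criteria after the screening phase will be randomly assigned to one of two groups". Both characteristics are therefore established before the envelope is opened, and ulcer history is among the screening assessments.

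The Primary Endpoint paragraph words the outcome differently from the analysis section: "The primary outcome of the study will be the proportion of subjects who achieved improvement in wound healing".

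**The concern.** Eligible ulcers span a 13-fold range of duration (52/4) and a 2-fold range of area (10/5). Blocks of 12 keep the arm sizes equal but do nothing to balance duration or area. If long-standing or larger ulcers are less likely to close within the 4-week study, an arm that by chance receives younger ulcers will look better, and a 2×2 test cannot separate that from a treatment effect.

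The trial is open-label. If the baseline table shows an imbalance, an adjustment chosen at that point would be chosen with the data in view. It is credible only if it is written down beforehand. At stake are some power, and the reading of the primary result in trials where the arms differ at baseline.

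**Working it through.** **No figure to reproduce.** The document states no sample size, alpha, power, healing rate or prognostic strength.

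**Assumptions:** 60 or 120 patients, 1:1 in blocks of 12; two-sided 5%; 40% healing; duration log-uniform on 4 to 52 weeks; area uniform on 5 to 10 cm². The odds ratio for healing is 0.8 (weak) to 0.5 (strong) per doubling of duration, and 0.7 (weak) to 0.4 (strong) per doubling of area.

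**Step 1. How often are the arms imbalanced in duration?**
- SD of log2 duration = log2(13)/√12 = 3.70/3.46 = 1.07.
- SE of the between-arm difference in means = 2 × 1.07/√N = 0.276 at 60 and 0.195 at 120.
- A 1.25-fold ratio of geometric means is log2(1.25) = 0.322. Then z = 0.322/0.276 = 1.17, two-sided probability 24%, at 60; and z = 0.322/0.195 = 1.65, probability 10%, at 120.
- A 1.5-fold ratio is log2(1.5) = 0.585. Then z = 2.12, probability about 3%, at 60; and z = 3.00, probability about 0.3%, at 120.

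**Step 2. How far does an imbalance move the crude difference?**
- Shift ≈ |log odds ratio per doubling| × imbalance in doublings × mean of p(1−p). At 40% healing that mean is about 0.24 (weak) or 0.21 (strong).
- 1.25-fold, weak: 0.223 × 0.322 × 0.24 = 1.7 points. Strong: 0.693 × 0.322 × 0.21 = 4.7 points.
- 1.5-fold: about 3 to 9 points, but rare by Step 1.
- For scale, the SE of the crude difference at 60 patients is √(0.4 × 0.6 × 2/30) = 12.6 points.

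**Step 3. What does adjustment change?** Simulation of the same design, 10,000 trials per setting: chi-square against logistic regression on arm, log duration and log area.

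| Strong covariates | 60 crude | 60 adjusted | 120 crude | 120 adjusted |
|---|---|---|---|---|
| Null rejection, trials with ≥1.25-fold imbalance | 7.1% | 5.6% | 8.1% | 5.1% |
| Power, 25-point difference | 0.50 | 0.55 | 0.81 | 0.84 |

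With weak covariates, power changes by about half a point. Over all randomisations the crude test rejects a true null in about 5.0% of trials. The adjusted score test rejects in about 5.6% at 60 patients and about 5% at 120.

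A repeat with 15,000 trials per setting, using the score test, agreed. Among imbalanced trials, null rejection was 7.9% crude against 5.5% adjusted at 60, and 8.3% against 4.6% at 120. Power rose by 4.4 and 3.9 points. With weak covariates it changed by less than half a point, and overall null rejection of the score test at 60 was 5.6% (strong) and 6.0% (weak).

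**The case against.** **The planned test is valid.** A reader might infer that the crude test is biased or that its type I error is inflated. The document does not support that. Under randomisation, chance imbalance is already part of the test's error rate, and simulation puts the overall rate at about 5%. The error is conditional on an imbalance having occurred. This stands in full.

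**The size depends on unstated quantities.** Nothing in the document says how strongly duration or area predicts 4-week healing. If the relation is weak there is essentially no gain. This stands too, and is why a range is given. A reader might also fix on the 3-to-9-point shift, but it needs a 1.5-fold imbalance, which is rare even at 60 patients. The 1.25-fold figures are the ones to use.

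**Why these two covariates?** HbA1c and perfusion are also in Table 1, and nothing there ranks them below ulcer age and size. This stands in part. Perfusion may be documented by any one of several methods, so it has no common scale. HbA1c would be a defensible addition. Area has only a 2-fold range, so duration carries most of the argument.

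**Is duration in weeks actually recorded?** Eligibility needs only a check against 4 and 52 weeks, and the screening list mentions ulcer history without saying that weeks are noted. This is fair, and the fix must say so explicitly.

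**Adjustment is not free.** At 60 patients the score test slightly exceeds 5%, the likelihood-ratio test rather more (5.7 to 5.9%), and a Wald test with a normal reference reaches 6 to 7%. One test must therefore be named.

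**Conclusion.** The point holds as one of precision and conditional protection, not validity. The only planned primary comparison ignores two baseline characteristics that eligibility requires to be established before assignment, and the randomisation does not balance them.

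Under the stated assumptions, roughly one trial in four of 60 patients, or one in ten of 120, has at least a 1.25-fold imbalance in duration. With strong covariates, null rejection in those trials is about 7 to 8% crude against 5 to 6% adjusted, and power at a 25-point difference rises by about 3.5 to 5 points. With weak covariates there is no material gain or loss. The change is worth making because it is cheap and cannot credibly be made after baseline data are seen.

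The figures assume a healed/not-healed outcome at 40%. They need not carry over if the primary outcome turns out to be improvement rather than healing.

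**What to change.** 1. First reconcile the Primary Endpoint paragraph (improvement in healing) with the Statistical analysis section (healing achieved), so that the model has one defined binary outcome.
2. Make the primary test a logistic regression of that outcome on arm, log ulcer duration in weeks and log baseline area, both continuous. Test arm by the score test at a stated two-sided level.
3. Report the standardised risk difference: average the predicted probabilities over all patients under each arm, and subtract.
4. State that duration in weeks is recorded at screening as part of the ulcer history.
5. If the model does not converge, use a Cochran-Mantel-Haenszel test with cut-points fixed before data are seen. The geometric midpoints of the eligible ranges, √(4 × 52) ≈ 14 weeks and √(5 × 10) ≈ 7 cm², would serve.
6. Keep one unadjusted chi-square test as the supportive analysis, and remove the open choice between chi-square and Fisher.

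Cost: SAP wording and one explicit screening entry, with no extra patients or procedures. Overall null rejection is about 5.6% rather than 5.0% at 60 patients (about 5% at 120), and there is little or no gain if the covariates are weakly prognostic.
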